## **6.2 DURATION OF STUDY PARTICIPATION**

### **6.2.1 Duration of study participation for each patient**

All patients will participate in a Screening period of up to 14 days. The study observation period starts at Randomization and lasts until the end of the study (the last study visit [eg, Follow-up Visit for patients who complete study treatment per protocol, or Study Closeout Visit for patients who prematurely permanently discontinue study treatment] of patient). The study is event-driven, therefore the duration will be determined as described in [Section 6.1.2](#).

The estimated study duration will be approximately 3 to 32 months, assuming approximately 29 months of recruitment, and approximately 3 months of follow-up after the last patient is randomized.

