# 1 OVERVIEW AND INVESTIGATIONAL PLAN

## 1.1 BACKGROUND

SOLOIST is a Phase 3, multicenter, randomized, double-blind, placebo-controlled, parallel group, stratified study of sotagliflozin for the treatment of patients with worsening heart failure.

After screening, patients who met all eligibility criteria were centrally randomized via in a 1:1 ratio to sotagliflozin or placebo at randomization visit. Randomization was stratified by baseline left ventricular ejection fraction (LVEF) (LVEF<50% and LVEF≥50%) and region (North America, Latin America, Western Europe, Eastern Europe, and rest of the world).

The original plan was to randomize approximately 4000 patients. However, SOLOIST enrollment was closed in March 2020 before meeting this objective.

A recent publication in the Journal of the American College of Cardiology discussed how clinical trials and programs have been disrupted by the COVID-19 pandemic. It provided the sotagliflozin program as an example where clinical trials have been prematurely terminated. Recommendations included careful consideration of statistical issues relating to potential loss of power, increased variability in data, and challenges in adjudication of events. Similarly, the FDA has issued guidance specific to COVID-19 recognizing the potential for disruption of clinical trials and identifying some of the data and statistical issues that need to be addressed by investigators and sponsors.

This plan describes statistical efficacy analyses to be conducted by an independent academic statistician and separately verified by the Lexicon statistical team. It addresses issues related to the early termination of SOLOIST. These issues have been reviewed and the recommended steps have been chosen in a blinded fashion without the use of any unblinded interim analysis.

The termination of enrollment and follow-up of SOLOIST did not allow enough time to amend the study protocol. Changes to the intended analysis plan are reflected in this document, rather than the protocol, and this plan takes precedence where there are differences between the two documents.

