##### 2.4.4.1 Analyses of primary efficacy endpoint

The analysis of the primary efficacy endpoint will be the comparison between the two treatments using a Wald test stratified by region (North America, Latin America, Western Europe, Eastern Europe, and rest of world) and LVEF (<50%, ≥50%). This primary comparison will be a 2-sided test at the 0.05 type 1 error level for the following hypothesis:

H0: HR=1 versus H1: HR ≠1

The estimates of the hazard ratio (HR) and corresponding 2-sided 95% confidence interval (CI) will be provided by a marginal Cox proportional hazard model stratified by region and ejection fraction, with non-cardiovascular (non-CV) death treated as a competing event. By using a robust sandwich covariance matrix estimate, the model allows for the possibility of multiple events within a given patient. If a given patient has more than one event on a given day, the event times will be varied by 0.1 day so that every event time is unique.

To determine whether the treatment effect on the primary endpoint is different before and after 240 days (the end of the window for up-titration of dose), a marginal proportional hazards model that allows the treatment HR to vary before and after 240 days will be compared with the model in which the treatment HR is assumed constant over time, to test whether a nonconstant HR provides a better fit to the observed data.

As a sensitivity analysis, an on-treatment analysis will be performed for the primary endpoint, using the same method above but only including events through 30 days after last dose. Another on-treatment sensitivity analysis will include only events through 7 days after last dose.

The cumulative incidence function (CIF) will also be constructed to estimate the primary efficacy endpoint rate by treatment group. The absolute risk reduction (ARR) will be estimated by the difference between treatment groups in the number of events per 100 patient-years of follow-up. Results will be provided for both the primary efficacy endpoint overall and its individual components (CV death, HHF, urgent HF visit). In addition, a figure summarizing the numbers of first and subsequent events will be constructed for the primary endpoint. Bars for sotagliflozin and placebo will be provided for the numbers of first events, second events, and a category of “third and subsequent events.” Within each bar the number of CV death, HHF, and urgent HF visit events will be separated by color.

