#### ***2.4.4.4 Additional efficacy analysis(es)***

Time-to-event other efficacy endpoints will be analyzed using the same statistical methodology as for the primary endpoint. If the endpoint concerns the first event, then only the first event experienced by a given patient will be included in the analysis. Deaths that are not part of a given endpoint will be treated as competing events.

For the analyses of DAOH and PDAOH, total potential follow-up time for each patient is defined as the number of days from date of randomization until the patient's date last known alive, or May 1, 2020 (the date sites were instructed to complete end of study contacts with patients; patients known to have died after this date will be censored as alive as of May 1, 2020) if the patient died. The total number of days spent in hospital will be derived from the investigator reports. If a patient died, the number of days dead will be calculated as the time interval between their date of death and May 1, 2020. DAOH will be calculated by subtracting days in hospital and days dead from total potential follow-up time; if a patient survived without hospitalization, DAOH will be equal to the potential follow-up time for that patient.

DAOH, days dead, and days in hospital will be compared between treatment groups by rate ratios (RRs) from a Poisson regression model with a log link function and Pearson  $\chi^2$  scaling of standard errors to account for potential overdispersion. In addition to treatment group, the logarithm of potential follow-up time will be used as an offset variable in the model. Given the expectation that a fraction of patients will survive without hospitalization until the end of follow-up (i.e., PDAOH =100%), PDAOH will be compared between treatment groups with one-inflated beta regression. In this application, the model will jointly estimate the treatment odds ratio (OR) of surviving until the end of the study without hospitalization (ie, PDAOH =100%), and the treatment OR of higher mean PDAOH among the subset of patients who died or had at least one hospitalization or died during follow-up (i.e., PDAOH <100%). Plots of the distribution of DAOH will be constructed,

as well as summaries of reasons for hospitalizations (e.g., HF, other efficacy event, non-efficacy adverse event, etc.).

Changes from baseline in NT-proBNP, hematocrit, HbA1c, body weight, and SBP will be analyzed using the same methods as for change in eGFR.

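### Pearson-scaled Poisson standard errors are too small for DAOH and days dead when follow-up varies widely, so nominal 95% intervals cover roughly 87–92%

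*SAP*

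**What the plan says.** SAP 2.4.4.4 states that "DAOH, days dead, and days in hospital will be compared between treatment groups by rate ratios (RRs) from a Poisson regression model", using a log link and Pearson chi-square "scaling of standard errors to account for potential overdispersion". It adds that "the logarithm of potential follow-up time will be used as an offset variable in the model". No robust variance is named for this model.

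The outcomes are built from the same follow-up time. For a patient who died, "the number of days dead will be calculated as the time interval between their date of death and May 1, 2020". Then "DAOH will be calculated by subtracting days in hospital and days dead from total potential follow-up time". Potential follow-up runs from randomization to May 1, 2020 for patients who died, and to the patient's own date last known alive otherwise.

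On the spread of follow-up, Protocol 6.2.1 planned that "The estimated study duration will be approximately 3 to 32 months". SAP 1.1 reports that "SOLOIST enrollment was closed in March 2020 before meeting this objective".

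DAOH is listed among the other efficacy endpoints (SAP 2.1.3.3). Days dead appears only in the analysis text of 2.4.4.4.

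**The concern.** With the offset, the fitted mean is proportional to follow-up T. Pearson scaling multiplies every patient's Poisson variance by one common factor, so the variance is also taken as proportional to T. The scaling corrects the average level of overdispersion but cannot correct a variance that rises faster than T.

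Days dead has such a variance. A death at time s contributes T − s dead days and a survivor contributes none, so the longest-followed patients supply most of the real variability. DAOH inherits this because it subtracts days dead from T. When T varies several-fold, the common factor understates the variance of the rate ratio. The estimate itself is not at issue. What suffers is the reported precision: intervals too narrow, and any nominal p-values too small, for an outcome that SAP Appendix D added to show clinical relevance.

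**Working it through.** The plan gives no figure for this analysis, so there is none to reproduce.

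**Inputs from the documents.** Model, offset, scaling and outcome definitions: SAP 2.4.4.4. Shortest follow-up: a patient enrolled in March 2020 has 31–61 days to May 1, 2020. Longest follow-up is not stated; the first protocol version is dated 05-Jan-2018, 847 days (just under 28 months) before the cut-off. Allocation is 1:1.

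**Assumptions.** The documents do not give the number randomized, mortality, accrual pattern or longest follow-up. Ranges used: 600–4000 patients, mortality 8–25% per year, longest follow-up 16–32 months.

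**Formulas.** With two arms and an offset, the rate in each arm is ΣY/ΣT. Let μ be the fitted mean and e = Y − μ.
- Scaled variance of the log rate ratio: φ(1/ΣY₁ + 1/ΣY₀), with φ = Σ(e²/μ)/(N − 2).
- Sandwich variance: Σe²/(ΣY)² in each arm, added over arms.
- If e² is proportional to Tᵏ, true variance / scaled variance = E[Tᵏ] / (E[T]·E[Tᵏ⁻¹]).

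With a constant, low death rate λ, E[e²] ≈ λ∫₀ᵀ(T − s)²ds = λT³/3, so k = 3. If deaths occur soon after randomization, k is near 2. Pearson scaling is right only for k = 1.

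**Closed form, T uniform on 60–670 days, k = 3.** E[T] = 365, E[T²] = 164,233, E[T³] = 8.258 × 10⁷. Ratio = 8.258 × 10⁷ / (164,233 × 365) = 1.38. True SE / stated SE = √1.38 = 1.17. Two-sided rejection rate = 2[1 − Φ(1.96/1.174)] = 9.5%, that is, 90.5% coverage.

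**Closed form, T uniform from near zero.** k = 2: (1/3)/(1/2)² = 1.33, giving 9.0%. k = 3: (1/4)/[(1/3)(1/2)] = 1.50, giving 11.0%.

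**Closed form, T uniform on 180–670 days.** E[T] = 425, E[T²] = 200,633, E[T³] = 1.0228 × 10⁸. k = 2: 200,633/425² = 1.11, giving 6.3%. k = 3: 1.0228 × 10⁸ / (200,633 × 425) = 1.20, giving 7.4%.

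**Null simulations** (mostly 4000–6000 replicates per row). The formula for the scaled SE matched a fitted Poisson regression with Pearson scaling (0.2398 both ways). Unless stated, N = 1200 and mortality is 15% per year.

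| Scenario | DAOH, scaled | Days dead, scaled |
|---|---|---|
| T 1.3–22 months | 9.4% | 9.2% |
| T 1.3–16 months, front-loaded hazard | 8.3% | 8.6% |
| T 1.3–27 months | 10.4% | 10.3% |
| Mortality 8% / 25% per year | 9.5% / 9.1% | 9.3% / 9.1% |
| Accrual weighted to late entry | 13.1% | 12.8% |
| SAP's T rule, 3% / 10% lost early | 10.4% / 10.8% | 10.6% / 11.0% |
| Planned 3–32 months, N = 4000 | 9.2% | 9.1% |
| Control: T 10–14 months | 5.4% | 5.2% |
| Control: T fixed at 12 months | 5.7% | 5.4% |

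For T of 180–670 days, simulations gave 6.4–7.6%.

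In the first row the true standard deviation is about 1.18 times the stated SE. With the sandwich variance on the same rate ratio, rejection is 4.6–5.7% for both outcomes in every scenario. Days in hospital under the SAP's scaling gave 3.2–7.1%. The excess disappears when follow-up is nearly equal and when the sandwich is used, which isolates the cause.

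**The case against.** A reader might infer that a specified 5% test of DAOH has nearly double its stated error rate, so that a chance benefit would be declared significant. The documents do not support that. SAP 2.4.4.4 says only that the outcomes are compared by rate ratios. The two-sided 0.05 level is set for the primary comparison (2.4.4.1) and the secondary hierarchy (2.4.4.3), and neither DAOH nor days dead is in that hierarchy. Protocol 11.4.2.3 calls the analysis of other endpoints descriptive, and 11.4.2.4 allows nominal p-values for them for description only. This objection stands: the consequence is under-coverage of a supportive interval.

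The stakes are limited in other ways. The same SAP section plans a one-inflated beta regression for percent DAOH and plots of the DAOH distribution, and all-cause mortality has its own time-to-event analysis. The size also depends on inputs that the documents do not give, so it must be a range.

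It is also tempting to call the SAP inconsistent, because for the primary endpoint it says: "By using a robust sandwich covariance matrix estimate, the model allows for the possibility of multiple events within a given patient". That sandwich is there for repeated events within a patient. Here each patient has one record and the problem is a misspecified variance, so 2.4.4.1 shows that the tool is in use but not that the SAP contradicts itself.

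Finally, follow-up does not end on one calendar date: survivors stop at their own date last known alive. Simulating that rule gave 10.4–11.0% in the early-stop setting, so it does not remove the problem.

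**Conclusion.** The point holds as a precision error in a supportive analysis. Under wide follow-up (from about 1–2 months to 16–27 months) and mortality of 8–25% per year, nominal 95% intervals for the DAOH and days-dead rate ratios cover about 87–92%, centrally about 91%. That equals a rejection rate of about 8–13% for a comparison made at a nominal 5%; the top of the range needs accrual weighted to late entry. With a spread of about 6–22 months the rate is about 7%, but enrollment up to March 2020 makes a six-month minimum implausible. The direction is secure, because it follows from the SAP's own definitions. The size rests on the assumed accrual, mortality and longest follow-up. Days in hospital is close to nominal. No primary or secondary conclusion is affected.

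**What to change.** In SAP 2.4.4.4, keep the log-link Poisson mean model and the log follow-up offset, and replace the Pearson chi-square scaling with a robust (sandwich) variance, one record per patient, for DAOH and days dead. Apply it to days in hospital as well, for consistency. It would also help to say that the intervals and any p-values for these outcomes are nominal.

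The cost is one phrase and one software option. Rate ratios do not change. Intervals for DAOH and days dead become roughly 10–25% wider: about 17–18% in the central case, and 27% in the late-entry scenario (0.0176/0.0139 for DAOH).

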#### ***2.4.4.2 Analyses of secondary efficacy endpoints***

Methods for controlling the overall type-I error rate when testing the secondary efficacy endpoints are described in Section 2.4.4.3 *Multiplicity issues*.

Time-to-event secondary efficacy endpoints will be analyzed using the same statistical methodology as for the primary endpoint. Deaths that are not part of a given endpoint will be treated as competing events.

As with the primary endpoint, the absolute risk reduction (ARR) of time-to-event secondary endpoints will be estimated by the difference between treatment groups in the number of events per 100 patient-years of follow-up. For those secondary endpoints which are a composite of events, results will be provided for both the overall composite and its individual components.

Absolute change in KCCQ-12 scores from baseline to Month 4 will be analyzed by analysis of covariance (ANCOVA) with treatment group as factor and baseline KCCQ-12 score and randomization stratification factors as covariates. The last available post-baseline score will be

carried forward to Month 4 if the patient is alive at Month 4 but the Month 4 value is missing. For patients who die, a worst score (0) will be imputed for the clinical summary score at all subsequent scheduled visits after the date of death where the clinical summary score would have been assessed.

The rate of decline in eGFR observed over time will be analyzed by repeated-measures mixed-effects models with absolute change in eGFR from baseline as the outcome, a random effect for intercept, and fixed effects for treatment, baseline value, and time. An additional model will be developed with an interaction between treatment and time. The variance-covariance matrix will be specified to be unstructured.

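### The eGFR-type mixed models omit the randomization strata, so the reported standard error for a constant treatment difference is slightly too large

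*SAP*

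**What the plan says.** SAP 1.1 describes the design: "Randomization was stratified by baseline left ventricular ejection fraction (LVEF) (LVEF<50% and LVEF≥50%) and region", with five regions, so there are 2 × 5 = 10 strata. Protocol 8.4 agrees.

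The SAP then uses these factors unevenly:

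- Primary endpoint (2.4.4.1): the comparison is made "using a Wald test stratified by region" and by LVEF. Time-to-event secondary and other endpoints follow the same method.
- KCCQ-12 (2.4.4.2): an ANCOVA with "baseline KCCQ-12 score and randomization stratification factors as covariates".
- eGFR (2.4.4.2, the next paragraph): a mixed model with "a random effect for intercept, and fixed effects for treatment, baseline value, and time". An additional model adds treatment by time. Neither names region or LVEF.
- NT-proBNP, hematocrit, HbA1c, body weight and SBP (2.4.4.4): the eGFR method again.
- DAOH, days dead and days in hospital (2.4.4.4): Poisson regression with Pearson scaling. "In addition to treatment group, the logarithm of potential follow-up time will be used as an offset variable in the model"; no other term is named.
- PDAOH (2.4.4.4): one-inflated beta regression. The treatment odds ratios are named, but no covariate list is given.

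Neither these sections nor SAP Appendix D gives a reason for the difference.

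**The concern.** When allocation is stratified, between-stratum variation no longer contributes to the variability of the treatment difference. A linear model without the strata still counts that variation as residual noise, so it reports a standard error larger than the true one, and its test rejects less often than the nominal level. In this SAP the affected models are the mixed models for eGFR and for the five variables that inherit its method.

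At stake are a little power, a confidence interval slightly too wide, and consistency within one efficacy section. SAP 1.1 and 1.3 say that enrollment closed before the planned 4000 patients and that the study is not powered for its design assumptions. A costless correction to the standard error is therefore worth having.

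**Working it through.** **The plan's own figures.** None is stated for these models, and SAP 1.3 says no new sample size calculation was made. The nearest design figure, 947 events in Protocol 11.1 (HR 0.81, 90% power, two-sided 0.05, 1:1), does reproduce: 4 × (1.95996 + 1.28155)² / (ln 0.81)² = 4 × 10.507 / 0.04440 = 947. It says nothing about the size of this point.

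**Inputs.** Ten strata and 1:1 allocation (SAP 1.1). Two-sided 0.05 (SAP 2.4.4.1 and 2.4.4.3). The share R² of residual variance explained by the strata, after the terms already in the model, is not in the documents. I assume 0.03 to 0.10 and show 0.01 to 0.15.

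**Constant treatment difference, linear model.** With balanced stratified allocation, the true variance of the estimate is proportional to 1 − R² whether or not the strata are fitted. The reported variance is proportional to 1 without them and to 1 − R² with them. Hence:

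- SE with / SE without = √(1 − R²): √0.97 = 0.985 and √0.90 = 0.949, a fall of about 1.5% to 5%.
- Type I error without strata = 2[1 − Φ(1.960/√(1 − R²))].
- For an effect with nominal 80% power: power without strata = Φ(0.842/√(1 − R²)); with strata = Φ(2.802/√(1 − R²) − 1.960).

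| R² | Fall in reported SE | Type I error without | Power without | Power with |
|---|---|---|---|---|
| 0.01 | 0.5% | 0.049 | 80.1% | 80.4% |
| 0.05 | 2.5% | 0.044 | 80.6% | 82.0% |
| 0.10 | 5.1% | 0.039 | 81.3% | 84.0% |
| 0.15 | 7.8% | 0.034 | 81.9% | 86.0% |

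**Simulated random-intercept model.** 600 patients, 10 strata, permuted blocks of 4, 60 runs; stratum effects and variance components assumed. The mean reported SE was 0.728 without strata and 0.695 with (4.7% smaller). The empirical SD of the estimate was 0.730 and 0.729 on the same data sets, so the estimate itself hardly changes. Sixty runs leave a relative error of about 1/√(2 × 59) = 9% in an empirical SD. The simulation therefore cannot show which reported SE is right; that rests on the formula above. It also used independent residuals, whereas the SAP asks for an unstructured covariance.

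**eGFR slope.** In the same simulation, the SE of the treatment-by-time contrast went from 1.335 to 1.331, about 0.3%. This contrast is largely within-patient, and strata entered as main effects absorb between-patient variation.

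**Poisson model with Pearson scaling.** 1200 patients, 500 runs, no treatment effect, assumed overdispersed counts of hospital days:

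| Stratum effects | Empirical SD, without / with | Reported SE, without / with | Null rejection, without / with |
|---|---|---|---|
| Moderate | 0.141 / 0.141 | 0.122 / 0.115 | 9.2% / 12.2% |
| Strong | 0.151 / 0.149 | 0.140 / 0.115 | 7.4% / 13.8% |

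Here the reported SE is too small even without the strata, the reverse of the linear case, and adding them shrinks it further. The rejection rates carry a Monte Carlo error of roughly one percentage point (√(0.05 × 0.95/500) = 1.0%).

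**PDAOH.** No arithmetic applies. Odds ratios are non-collapsible, so adding strata changes the quantity estimated and need not reduce its standard error.

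**The case against.** The strongest reply is that little is lost. Stratified randomization has already delivered the balance, the estimate is as precise without the strata, and the test errs on the safe side. The endpoints also carry little weight. eGFR decline is the last of seven secondary endpoints in SAP 2.1.3.2, which sets the testing order. The other variables are listed in 2.1.3.3, outside that order, and Protocol 11.4.2.3 treated other endpoints as descriptive. No document commits the sponsor to fitting the strata in every model. All of this stands, and it limits the point to a minor one. It does not make the reported standard error correct or explain why adjacent paragraphs differ.

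A reader might also infer more than the documents support:

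- *The omission wastes precision worth 3% to 10% more patients.* It does not. The estimate is no more variable; only its reported standard error is inflated. At R² of 0.05 to 0.10 the power difference is 1.4 to 2.7 percentage points.
- *The secondary eGFR endpoint is materially weakened.* Rate of decline is a treatment-by-time contrast, and there the change is about 0.3%.
- *The same loss affects DAOH, days dead and days in hospital.* The √(1 − R²) rule belongs to linear models. The simulated Poisson results run the other way, although they depend on assumed data.
- *The PDAOH model excludes the strata.* The SAP gives no covariate list for it, so the model is under-specified and nothing more can be concluded.

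**Conclusion.** The point holds for the linear mixed models when they estimate a constant treatment difference. The reported standard error is about 1.5% to 5% too large if the strata explain 3% to 10% of residual variance, and the actual type I error is 0.044 to 0.039 at R² of 0.05 to 0.10. The size rests wholly on that assumed share, and the direction rests on allocation having been balanced within strata as the SAP describes. For the eGFR slope the case is consistency alone. No precision claim is made for the Poisson or beta models. No confirmatory conclusion depends on DAOH, PDAOH or the five inherited change variables, so this is a desirable improvement and not a flaw that threatens the trial's conclusions.

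**What to change.** In SAP 2.4.4.2, add region (five levels) and LVEF (<50%, ≥50%) as fixed effects to both eGFR mixed models. Section 2.4.4.4 then carries them over to NT-proBNP, hematocrit, HbA1c, body weight and SBP. Alternatively, state why they are left out.

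For DAOH, days dead and days in hospital, adding the strata is optional. If they are added, replace reliance on Pearson scaling alone with a robust (sandwich) variance. For PDAOH, list the covariates of both parts of the beta regression. If region and LVEF are among them, say that the odds ratios are conditional on those factors.

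The cost is SAP wording, two factors per mixed model (4 + 1 = 5 degrees of freedom) and, for the Poisson models, a variance option. No new data are needed.

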## 11 STATISTICAL CONSIDERATIONS

### 11.1 DETERMINATION OF SAMPLE SIZE

The study is powered by primary endpoints of time to first occurrence of CV death or HHF in patients with LVEF <50%, and in the total patient population. In order to achieve the target number of events of 947 first occurrence of CV death/HHF in patients with LVEF <50% and 1341 first occurrences of CV death/HHF in the total patient population, it is estimated that approximately 4000 patients will be randomized over an estimated 29 months of recruitment period with approximately 3 months of follow-up after the last patient is randomized.

The sample size calculation is based on the following trial design assumptions:

- A recruitment period of approximately 29 months
- Approximately 3 months of follow-up after the last patient is randomized
- 29.2%, 39.7% and 44.5% event rate by Month 6, Month 12, and Month 24, respectively, in the placebo group (by assuming yearly hazard rate at Months 1, 2, 3, 4, 5, 6, 12, 24, and 36 be 1.06, 0.87, 0.74, 0.62, 0.49, 0.36, 0.32, 0.08, and 0.05, respectively)
- Hazard ratio (HR) = 0.81 for sotagliflozin versus placebo for patients with LVEF <50% and for patients with LVEF  $\geq$ 50%
- 2% annual censoring rate

This will provide:

- 90% power (with  $\alpha=0.05$ , 2-sided) to demonstrate superiority of the primary endpoint (first occurrence of CV death or HHF) comparing sotagliflozin versus placebo in patients with LVEF <50%.
- More than 90% power (with  $\alpha=0.05$ , 2-sided) to demonstrate superiority of the primary CV endpoint (first occurrence of CV death or HHF) comparing sotagliflozin versus placebo in the total patient population.

This is an event-driven study. Therefore, the study will continue until approximately 947 primary events (first occurrence of CV death or HHF) have been positively adjudicated in patients with LVEF <50%, AND approximately 1341 primary events (first occurrence of CV death or HHF) have been positively adjudicated in total patient population, and  $\geq$ 3 months follow-up for the last randomized patient.

Calculations were based log-rank test with user defined survival, accrual and drop-out rates by using EAST 6.4.

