### ***2.1.3.3 Other efficacy endpoints***

- First occurrence of CV death, HHF, or urgent visit for HF
- First occurrence of CV death or HHF
- Total occurrences (first and potentially subsequent) of HHF after randomization
- Total occurrences (first and potentially subsequent) of urgent HF visits after randomization
- First occurrence of CV death, HHF, urgent visit for HF, non-fatal myocardial infarction, and non-fatal stroke
- First occurrence of fatal and non-fatal MI
- First occurrence of fatal and non-fatal stroke
- First occurrence of new onset of atrial fibrillation or atrial flutter (adverse events (AEs) with a preferred terms (PTs) of atrial fibrillation or atrial flutter)
- First occurrence of a composite renal endpoint, consisting of events sustained  $\geq 50\%$  decrease in eGFR from baseline (for  $\geq 30$  days), chronic dialysis, renal transplant, or sustained eGFR  $< 15$  mL/min/1.73m^2 (for  $\geq 30$  days)
- First occurrence of severe hypoglycemia
- Total occurrences of the following hypoglycemia categories
  - Severe hypoglycemia
  - Hypoglycemia with documented glucose value  $< 54$  mg/dL
  - Hypoglycemia with documented glucose value  $< 70$  mg/dL
- Days alive and out of hospital (DAOH) and percent DAOH (PDAOH)

- Changes from baseline in NT-proBNP, hematocrit, HbA1c, body weight, and SBP

All time-to-event endpoints are assessed based on investigator-reported events.

Cardiovascular death includes death of undetermined cause.

The first occurrence of the composite renal endpoint is defined as follows:

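### The PDAOH = 100% part of the one-inflated beta regression has no follow-up term, which gives up a modest amount of power on an exploratory endpoint

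*SAP*

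**What the plan says.** SAP 2.1.3.3 lists "Days alive and out of hospital (DAOH) and percent DAOH (PDAOH") among the other efficacy endpoints, outside the fixed test sequence of SAP 2.4.4.3.

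SAP 2.4.4.4 then sets out two models.

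- **DAOH, days dead and days in hospital:** a Poisson model with treatment group, in which "the logarithm of potential follow-up time will be used as an offset variable in the model".
- **PDAOH:** "PDAOH will be compared between treatment groups with one-inflated beta regression". One part estimates "the treatment odds ratio (OR) of surviving until the end of the study without hospitalization (ie, PDAOH =100"%). The other estimates a treatment odds ratio for mean PDAOH among patients below 100%. No covariate, follow-up term or stratification factor is named for either part.

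On the follow-up window, "total potential follow-up time for each patient is defined as the number of days from date of randomization until" the date last known alive for survivors, or May 1, 2020 for patients who died.

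Two statements bear on how widely follow-up varies. The protocol (6.2.1) planned for a wide range: "The estimated study duration will be approximately 3 to 32 months". The SAP (1.1) reports that "SOLOIST enrollment was closed in March 2020 before meeting this objective".

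**The concern.** The 100% part treats every patient as one yes/no trial. A patient randomized in March 2020 has 31 to 61 days to May 1, 2020, and scores 100% by staying alive and out of hospital for that time. A patient enrolled early must do so for much longer to get the same score. Dividing by follow-up does not help here, because both patients score exactly 100%.

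Calendar time from randomization to the stop date is fixed at randomization, so it is balanced between arms in expectation, and leaving it out does not bias the test. What is lost is power, because a known source of variation stays in the error. The SAP (1.3) already concedes that early termination left the study without its planned power. At stake is the sensitivity of one supportive analysis. No primary or hierarchical result is touched.

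**Working it through.** The documents give no power or precision figure for PDAOH. The check therefore starts from the protocol's hazards and then varies what is unknown.

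**1. Reproduce the plan's own figures.** Protocol 11.1 assumes for placebo a "yearly hazard rate at Months 1, 2, 3, 4, 5, 6, 12, 24, and 36 be 1.06, 0.87, 0.74, 0.62, 0.49, 0.36, 0.32, 0.08"; the remaining value, for Month 36, is 0.05. Read each value as the hazard over the interval ending at that month.

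- Cumulative hazard at Month 6: (1.06 + 0.87 + 0.74 + 0.62 + 0.49 + 0.36)/12 = 0.345
- At Month 12: 0.345 + 0.32 × 6/12 = 0.505
- At Month 24: 0.505 + 0.08 = 0.585

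The event rates 1 − exp(−H) are 29.2%, 39.6% and 44.3%, against 29.2%, 39.7% and 44.5% stated. The event target also reproduces: 4 × (1.960 + 1.282)² / (ln 0.81)² = 947.

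**2. How the event-free chance depends on follow-up.** For CV death or HHF, exp(−H) is:

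| Months | 1.5 | 3 | 24 | 32 |
|---|---|---|---|---|
| Chance | 0.88 | 0.80 | 0.56 | 0.54 |

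PDAOH counts hospitalization for any reason, so its hazard is higher. Its size and shape are not in the documents. With a constant 0.7 per year, the chance is 0.92 at 1.5 months and 0.25 at 24 months.

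**3. Power given up.** For a randomized treatment and a prognostic covariate T (follow-up) in a logistic model, the gain in effective sample size is approximately

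gain = 1/(1 − R²) − 1, with R² = Var[p(T)] / [p̄(1 − p̄)],

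where p(T) is the chance of 100% at follow-up T and p̄ is its mean. Uniform entry is assumed.

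Example: protocol shape × 1.5, follow-up 1.5 to 24 months. Here p̄ = 0.515, Var[p(T)] = 0.0103 and R² = 0.0103/(0.515 × 0.485) = 0.041, so the gain is 4.3%.

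| Assumed hazard | Follow-up (months) | Gain |
|---|---|---|
| Protocol shape × 1 to × 3 | 3 to 32 | 1.8% to 3.9% |
| Protocol shape × 1 to × 3 | 1.5 to 12, 20, 24 or 28 | 2.7% to 7.5% |
| Constant 0.3 to 1.4 per year | 1.5 to 24 | 7.9% to 27.9% |
| Constant 0.3 to 1.4 per year | all ranges tried | 3.3% to 32.0% |

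**4. Simulation of the 100% part**, without and with follow-up. Assumed: N = 1200, follow-up 1.5 to 24 months, true hazard ratio 0.75.

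| Hazard | Power without | Power with | (ratio of mean z)² |
|---|---|---|---|
| Protocol shape × 1.5 | 88.5% | 89.0% | 1.05 |
| Constant 0.7 per year | 79.5% | 84.0% | 1.18 |
| Constant 1.0 per year | 83.3% | 90.0% | 1.21 |

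A further simulation gave about 3% to 4% with the protocol's shape and 13% at a constant 0.7 per year. The constant-hazard figures are therefore approximate.

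**5. Validity.** Under no effect, the unadjusted test rejected in 5.5% of 400 runs and the adjusted test in 6.0%. The simulation error is √(0.05 × 0.95/400) = 1.1 percentage points, so both agree with 5%.

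**6. What happens to the odds ratio.** At a constant 0.7 per year the log odds ratio moves from 0.327 (SE 0.116) to 0.386 (SE 0.126). The SE rises and the estimate rises more, so mean z goes from 2.81 to 3.06.

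**7. The part below 100%.** No useful gain: the empirical SD of the treatment coefficient was 0.065 without and 0.064 with follow-up.

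**The case against.** A reader might infer more than the documents support in three ways.

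- **That the PDAOH model ignores follow-up while the DAOH model uses it.** Not so. PDAOH is a percentage of potential follow-up, so follow-up is its denominator. That is the counterpart of the Poisson offset, which is an exposure term with its coefficient fixed at 1 and not a precision covariate. The gap is confined to the binary 100% part.
- **That precision is being thrown away for nothing.** Step 6 shows the SE of the log odds ratio going up. Adjustment changes the target to a conditional odds ratio, and only power improves.
- **That adjustment would free the odds ratio from the enrollment pattern.** It would not. With the protocol's hazards and a hazard ratio of 0.81, the 1.5-month chances are 0.883 and 0.883^0.81 = 0.904, an odds ratio of 1.25. At 24 months they are 0.557 and 0.557^0.81 = 0.623, an odds ratio of 1.31. A single treatment term remains an average over follow-up lengths.

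It can also be said that an unadjusted contrast is legitimate for a supportive endpoint, that the same paragraph already has follow-up-offset comparisons of DAOH, days dead and days in hospital, and that the larger gains need an assumed near-constant hazard. All of this stands, and it limits the point to an optional improvement.

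Last, a covariate running to May 1, 2020 does not match the outcome window of survivors, which ends at the date last known alive. That is true but matters little. With 2% annual loss, adjusting for either version gave nearly the same power (84.0% and 85.0% at a constant 0.7 per year). The SAP's own potential follow-up ends differently for deaths and survivors, so it depends on outcome and is the less clean choice.

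**Conclusion.** The point holds as one of efficiency. The SAP specifies no follow-up term for the PDAOH = 100% part, and the chance of that outcome falls with follow-up, which varies widely under staggered entry and a common stop. The unadjusted test is valid. The loss is about 2% to 8% of effective sample size with the protocol's hazard shape. It can reach roughly 30% only with a high constant hazard.

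These sizes rest on assumptions that the documents do not settle: the level and shape of the all-cause hospitalization and death hazard, uniform entry, the longest follow-up, and N = 1200 for the power figures. Given the endpoint's place outside the hierarchy, this is a cheap improvement. The documents do not support calling it an error or a source of bias.

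**What to change.** Add to SAP 2.4.4.4 that the PDAOH = 100% part includes the logarithm of days from randomization to May 1, 2020 as a covariate, and that its treatment odds ratio is conditional on follow-up length. Leave the part below 100% as it is, since nothing is gained there. Optionally, report a standardized risk difference for PDAOH = 100%, which is easier to interpret than either odds ratio.

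The cost is one covariate, computed from the randomization date. The odds ratio becomes conditional, with a larger SE and a larger estimate, and it still depends on follow-up length. The text should not present it as more precise.
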